7.3.3 TERMINATION VISIT

The following procedures and assessments should be performed on subjects who withdraw or are discontinued from the study.

- Pain NRS assessment
- WOMAC questionnaire
- PASS assessment
- SF-36
- Collection of AE and concomitant procedures/therapies/medication data
- Assessment of NSAID/acetaminophen usage

Protocol SM04690-OA-07
Biosplice Therapeutics, Inc.

AM02V00
04 May 2021

- Review of medical history
- Physical examination
- Knee examination
- Weight measurement
- Vital sign measurements (pulse rate and blood pressure)
- Venipuncture and collection of samples for clinical laboratory tests
- Radiograph – bilateral in weight-bearing fixed flexion position, PA view X-ray (if not completed within 12 weeks before the Termination Visit)

Note: Subjects who withdraw from the study after having a partial or total knee replacement are not required to complete the pain NRS assessment, WOMAC questionnaire, PASS assessment, SF-36, or radiograph.

7.3.4 SCHEDULE OF EVENTS TABLE

	Visit 1E (Day 1) + 6 weeks	Visit 2E (Week 24) ± 4 weeks	Visit 3E (Week 48) ± 4 weeks	Visit 4E Phone visit (Week 52) ± 7 days	Visit 5E, 7E, 9E, etc. (Week 74, 126, 178, etc.) ± 4 weeks	Visit 6E, 8E, 10E, etc. (Week 100, 152, 204, etc.) ± 4 weeks	Termin- ation Visit^d
Informed consent	X						
Inclusion & exclusion criteria	X						
Medical history							X
Urine pregnancy test ^a	X		X			X	
Injection into target knee ^b	X		X			X	
Physical examination ^c			X				X
Knee examination ^c		X	X		X	X	X
Weight ^c		X	X			X	X
Vital signs ^c		X	X			X	X
Clinical laboratory sampling ^c		X	X			X	X
Pain NRS	X	X	X		X	X	X
WOMAC		X	X		X	X	X
PASS	X		X			X	X
SF-36			X			X	X
Knee Radiograph		X	X		X	X	X ^e
Collection of biomarker samples ^c			X				
AEs and concomitant procedures/therapies/medications	X	X	X	X	X	X	X
Assessment of NSAID/acetaminophen usage ^c		X	X		X	X	X

Abbreviations: AEs, adverse events; NRS, numeric rating scale; PASS, Patient Acceptable Symptom State; SF-36, 36-Item Short Form Health Survey; WOMAC, Western Ontario and McMaster Universities Arthritis Index.

^a Urine pregnancy tests are to be performed on WOCBP only.

^b Study injection should be the last procedure performed at injection visits (e.g., Visit 1E, 3E, 6E, etc.).

^c Collection of NSAID/acetaminophen usage, physical and knee examination, weight measurement, vital sign measurements, and venipuncture and collection of samples for clinical laboratory tests and biomarker analysis will be performed at the parent-study Week 56 (EOS) visit and therefore do not need to be repeated at Visit 1E.

^d Subjects who discontinue from the study *after* having a partial or total knee replacement are not required to complete the pain NRS assessment, WOMAC questionnaire, PASS assessment, SF-36, or radiograph at the Termination Visit.

^e Radiograph is only to be performed at the Termination Visit, when applicable, if not performed within 12 weeks before the Termination Visit.

7.4 JUSTIFICATION FOR SENSITIVE PROCEDURES

Not applicable for this study.

7.5 CONCOMITANT MEDICATIONS, TREATMENTS, AND PROCEDURES

Details regarding the name, indication, route of administration, dose, and frequency of all parent-study medications will be recorded in this study. Changes to medications ongoing at Visit 1E will be recorded in this study. Changes to ongoing medications that occur after the parent-study EOS visit will not be recorded in the parent study. All new medications, therapies, or procedures taken or received from Visit 1E through the Termination Visit will be recorded in the eCRF at each visit. Documented medications should include prescription, over the counter, supplements, as well as herbal or alternative medications.

All new or modified concomitant medications must be recorded on the “Concomitant Medications” eCRF.

Procedures or non-drug therapies that are ongoing, new, or modified at or after Visit 1E must be recorded on the “Procedures and Non-Drug Therapies” eCRF.

AE assessments should include consideration of any new or modified concomitant therapies administered to the subject.

7.5.1 PRECAUTIONARY MEDICATIONS, TREATMENTS, AND PROCEDURES

Not applicable to this study.

7.6 PROHIBITED MEDICATIONS, TREATMENTS, AND PROCEDURES**Prohibited Concomitant Medications and Procedures:**

- Any IA injection, including glucocorticoids, hyaluronic acid derivatives, PRP, stem cell therapies, or other agents with therapeutic intent, into either knee is prohibited while the subject is on study; IA injection of glucocorticoids, hyaluronic acid derivatives, PRP, stem cells, or other therapeutic agents into joints other than the knee is allowed.
- The following medications are prohibited while the subject is in the study:
 - Opioids; short-term use of opioids as part of anesthesia or procedural sedation during the study period is permitted
 - Centrally acting analgesics (e.g., duloxetine) (refer to [Appendix 1](#))
 - Topical local anesthetic agents; short-term use as part of anesthesia, including for study injections during the study period is permitted
 - Other anticonvulsants not listed in [Appendix 1](#)
 - Systemic glucocorticoids ≥ 10 mg of prednisone per day or the equivalent; epidural, inhaled, intranasal, and topical glucocorticoids are permitted

- Drugs screened to assess eligibility in the parent study, unless clinically indicated and allowed by the protocol: amphetamine, buprenorphine, cocaine, methadone, opiates, phencyclidine, propoxyphene, barbiturates, benzodiazepine, methaqualone, and tricyclic antidepressants
- Electrotherapy (refer to [Appendix 1](#)), acupuncture, therapeutic ultrasound, and/or chiropractic treatments for knee OA are prohibited while the subject is on study.
- Any new formalized (i.e., prescribed by a medical professional) physical therapy exercise programs for knee OA are prohibited while the subject is on study.
- Elective surgery of the pelvis/hip, knee, ankle, or foot is prohibited while the subject is on the study.
- Subjects are prohibited from participating in any other clinical research trial that includes the receipt of an IP or any experimental therapeutic procedure. Subjects are also prohibited from participating in any observational research trial while in the study.

The Investigator should notify the Medical Monitor(s) immediately if any prohibited therapies are required to ensure subject safety.

7.7 PROPHYLACTIC MEDICATIONS, TREATMENTS, AND PROCEDURES

Not applicable to this study.

7.8 RESCUE MEDICATIONS, TREATMENTS, AND PROCEDURES

Subjects are allowed to use NSAIDs and/or acetaminophen for pain relief as needed. If a subject's clinical condition significantly deteriorates (defined as experiencing significant pain that cannot be satisfactorily controlled using NSAIDs and/or acetaminophen), the Investigator should consult with the Medical Monitor(s).

7.9 PARTICIPANT ACCESS TO STUDY AGENT AT STUDY CLOSURE

Not applicable to this study.

8. ASSESSMENT OF SAFETY

8.1 SPECIFICATION OF SAFETY PARAMETERS

Safety assessments include physical examinations, vital signs, clinical laboratory tests, collection of AEs and SAEs, concomitant medications, and general medical evaluations.

8.1.1 DEFINITION OF ADVERSE EVENTS

AEs in the eCRF will be classified according to the most recent US Food and Drug Administration (FDA) definitions and in a manner consistent with International Council for Harmonisation Guideline for Good Clinical Practice (ICH-GCP) guidelines. As such the following definitions will be used:

An AE is any unfavorable and unintended sign, symptom, or disease temporally associated with the use of an IP or other protocol-imposed intervention, regardless of attribution. An AE may include intercurrent illnesses or injuries that represent an exacerbation (increase in frequency, severity, or specificity) of preexisting conditions (e.g., worsening of asthma).

Whenever possible, it is preferable to record a diagnosis as the AE term rather than a series of symptoms relating to a diagnosis. Fluctuations of preexisting conditions, including the disease under study that does not represent a clinically significant exacerbation or worsening, need not be considered AEs. In order to classify AEs and diseases, preferred terms will be assigned by the Sponsor to the original terms entered on the eCRF, using the Medical Dictionary for Regulatory Activities (MedDRA).

In this protocol, signs and symptoms of exacerbation or worsening of target knee OA will be captured in the context of efficacy assessments and recorded on specific pages of the eCRF. Anticipated fluctuations or anticipated deterioration (in the opinion of the Investigator) of the underlying disease (target knee OA) will not be considered AEs nor captured on the AE eCRF.

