5.6.2 HANDLING OF PARTICIPANT WITHDRAWALS OR TERMINATION

All Termination Visit procedures and assessments should be performed on subjects who are withdrawn or who voluntarily withdraw, including subjects who withdraw due to partial or total knee replacement. The date the subject is withdrawn from the study and the reason for the discontinuation should be recorded on the electronic case report form (eCRF). The Investigator or designee must complete all applicable eCRFs for subjects who discontinue from the study.

Replacement of subjects who withdraw or discontinue is not allowed.

Total or Partial Knee Replacement Follow-Up

A subject who has had total or partial knee replacement of the target knee should be discontinued from the study. In addition to Termination Visit procedures, sites should make every attempt to follow up with these subjects approximately 6 months after the total or partial knee replacement surgery is completed to assess outcomes of the surgery.

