8.1.2 DEFINITION OF SERIOUS ADVERSE EVENTS

According to the ICH-GCP Guidelines E6 (R2), an SAE is any untoward medical occurrence during a clinical investigation that is characterized by one or more of the following:

- Results in death
- Is life threatening
- Requires inpatient hospitalization or prolongation of existing hospitalization
- Results in persistent or significant disability/incapacity
- Is a congenital anomaly/birth defect
- Is an important medical event, defined as an event that does not fit one of the other outcomes, but may jeopardize the subject and may require medical or surgical intervention (treatment) to prevent one of the other outcomes. Examples include allergic bronchospasm (a serious problem with breathing) requiring treatment in an emergency room (ER), serious blood dyscrasias (blood disorders), or seizure/convulsion that does not result in hospitalization. The development of drug dependence or drug abuse would be other examples of important medical events.

The term "life-threatening" in the definition of "serious" refers to an event in which the subject was at risk of death at the time of the event; it does not refer to an event which hypothetically might have caused death if it were more severe.

"Inpatient hospitalization" is clarified as hospitalization lasting ≥ 24 hours. Admission to the hospital or prolongation of hospitalization qualifies as an SAE only if it is the result of an AE.

All SAE information must be recorded on the SAE form approved by the Sponsor. Additional follow-up information (e.g., test results, autopsy, and discharge summary) may be requested to supplement the SAE report form and can be attached as de-identified records.

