9.6.3 PASS and Response Analysis

The number and percent of subjects reporting “Yes” to Patient Acceptable Symptom State (PASS) at Visit 3E (Week 48) and Visit 6E (Week 100) will be summarized. Logistic regression analysis will be implemented for “Yes” responses in PASS adjusted for their response at Visit 1E (Day 1), with 95% confidence intervals and P values reported.

The number and percent of subjects reporting Outcome Measures in Rheumatology Clinical Trials (OMERACT)-Osteoarthritis Research Society International (OARSI) ‘strict’ responders will be summarized. An OMERACT-OARSI ‘strict’ responder must have a 50% improvement with corresponding 20 point (out of 100) actual scale improvement in pain or function outcomes. Two ‘strict’ responder outcomes will be estimated, one using WOMAC Pain and WOMAC Function and the other using Pain NRS (2-point improvement out of 10) and WOMAC Function.

Additionally, the number and percent of subjects reporting 20% improvement, 30% improvement, 50% improvement, and 70% improvement in Pain NRS, WOMAC Pain, and WOMAC Function will be summarized. Logistic regression analysis will be implemented for improvement in these assessments as well, with 95% confidence intervals and P values reported.

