15.2 Appendix 2 – Estimands

	Estimator	Variable	Population	Intercurrent events	Population level summary
Primary	Main	Change from parent-study baseline in mJSW at Visit 3E (Week 48)	FAS	Prohibited medications and NSAID/acetaminophen use: treatment policy strategy; analysis will be conducted regardless of use of prohibited medications or NSAID/acetaminophen use.	Difference in the change from parent-study baseline between LOR and placebo using parent-study baseline-adjusted ANCOVA with available data.
	Sensitivity 1	Change from parent-study baseline in mJSW at Visit 3E (Week 48)	FAS	Prohibited medications and NSAID/acetaminophen use: treatment policy strategy; analysis will be conducted regardless of use of prohibited medications or NSAID/acetaminophen use.	Difference in the change from parent-study baseline between LOR and placebo using parent-study baseline-adjusted ANCOVA with missing data imputed using the MI method.
	Sensitivity 2	Change from parent-study baseline in mJSW at Visit 3E (Week 48)	mFAS	Prohibited medications and NSAID/acetaminophen use: treatment policy strategy; analysis will be conducted regardless of use of prohibited medications or NSAID/acetaminophen use.	Difference in the change from parent-study baseline between LOR and placebo using parent-study baseline-adjusted ANCOVA with available data.
	Sensitivity 3	Change from parent-study baseline in mJSW at Visit 3E (Week 48)	PPAS	1) Prohibited medications: principal stratum strategy; subjects who used prohibited medications will be excluded from this analysis. 2) NSAID/acetaminophen: treatment policy strategy; analysis will be conducted regardless of NSAID/acetaminophen use.	Difference in the change from parent-study baseline between LOR and placebo using parent-study baseline-adjusted ANCOVA.
Estimand is repeated using the OA-07-study baseline as Secondary					

Secondary	Estimator	Variable	Population	Other intercurrent events	Population level summary
	Main	Change from parent-study baseline in Pain NRS at Visit 3E (Week 48)	FAS	Prohibited medications and NSAID/acetaminophen use: treatment policy strategy; analysis will be conducted regardless of use of prohibited medications or NSAID/acetaminophen use.	Difference in the change from parent-study baseline between LOR and placebo using parent-study baseline-adjusted ANCOVA with available data.

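### Target-knee replacement is counted in no endpoint, estimand or efficacy analysis, and the worsening behind it can stay out of AE and SAE counts if the Investigator judges it anticipated

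*Protocol*

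**What the plan says.** **Safety definitions.** Protocol 8.1.1 states that "signs and symptoms of exacerbation or worsening of target knee OA will be captured in the context of efficacy assessments", and then that "Anticipated fluctuations or anticipated deterioration (in the opinion of the Investigator) of the underlying disease (target knee OA) will not be considered AEs". SAP 7.4.1 repeats this. Protocol 8.1.2 adds that "Admission to the hospital or prolongation of hospitalization qualifies as an SAE only if it is the result of an AE". Another sentence of 8.1.1 is narrower: it exempts fluctuations of existing conditions, "including the disease under study that does not represent a clinically significant exacerbation or worsening, need not be considered AEs". Protocol 7.1.1 requires a knee examination at every clinic visit after Visit 1E and sends clinically significant findings to the AE form. SAP 10.4 agrees for findings made after injection.

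**Replacement.** Protocol 5.6.2 says: "A subject who has had total or partial knee replacement of the target knee should be discontinued from the study". Sites are asked to try to follow these subjects up about 6 months after surgery. Protocol 5.6.1 lists replacement as its own discontinuation reason. Protocol 7.3.3 says: "Subjects who withdraw from the study after having a partial or total knee replacement are not required to complete the pain NRS assessment". The same waiver covers WOMAC, PASS, SF-36 and the radiograph.

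**Analysis.** The continuous outcomes are compared by baseline-adjusted ANCOVA (SAP 9.4 to 9.6.2). The binary outcomes in SAP 9.6.3 are PASS, strict response and percentage improvement: "20% improvement, 30% improvement, 50% improvement, and 70% improvement in Pain NRS, WOMAC Pain, and WOMAC Function will be summarized". In Appendix 2 the main estimators use available data, and the intercurrent-event entry reads "Prohibited medications and NSAID/acetaminophen use: treatment policy strategy". Knee replacement appears nowhere in that appendix.

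**The concern.** The primary objective is the safety and efficacy of a second year of an injection into the knee. SAP section 1 itself says that agents of this kind might delay or reduce the need for joint replacement. A replacement of the treated knee is therefore among the most informative single events the study can record, both as possible harm and as treatment failure.

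The plan gives it no settled place. Safety can pass it to efficacy through the carve-out for anticipated deterioration. Efficacy has no variable that receives it and no rule for the subject's missing outcomes. If subjects who go to replacement would have had worse values than those who stay, leaving them out makes an arm's mean mJSW change and its responder rates look better. The arm with more replacements gains more.

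**Working it through.** No figure in the plan bears on this point. The sample size of about 500 rests on practical grounds, with no power calculation, so there is nothing to reproduce. The check traces one subject through the plan and then gives an illustration of size.

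**1. Safety tables.** Take a subject whose target knee deteriorates to replacement.
- If the Investigator judges the deterioration anticipated, Protocol 8.1.1 keeps it off the AE form. With no AE, the admission does not meet 8.1.2 and is not an SAE. The target-knee AE/SAE table in SAP 10.1 shows only what reached the AE form.
- If the Investigator relies on the other sentence of 8.1.1, or on the knee-examination rule in 7.1.1, a clinically significant worsening can be recorded as an AE.
- The same event can thus be classified in two ways at two sites, each following the text.

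**2. Efficacy analyses.** Suppose the replacement falls before Visit 3E and the subject leaves after surgery.

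| Analysis | Rule | What happens to this subject |
|---|---|---|
| FAS ANCOVA at Visit 3E | Available data (Appendix 2) | No value required, so normally not in the estimate |
| MI on the FAS | MAR; regression on the baseline value (the formula also carries group), each timepoint separately (SAP 7.1.4) | Imputed like others with that baseline; a decline at Visit 2E is not used |
| mFAS | Completed Visit 3E (SAP 6.4) | Excluded |
| CAS | mJSW result at Visit 6E (SAP 6.5) | Excluded |
| PPAS | Completed Visit 6E (SAP 6.2) | Excluded |
| PASS, strict and improvement responders | No missing-data rule; evaluable numbers vary (SAP 7.1) | Normally outside the denominator |

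If a site did collect scores after surgery at a scheduled visit, SAP 7.1.3 would assign them to that visit. A score for a replaced knee could then enter as an ordinary outcome.

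**3. Size for mJSW (illustration).** Let f be the fraction of an arm lost through replacement and D the extra loss they would have shown relative to those remaining. The available-data mean is then too favourable by f × D. Neither quantity is in the documents. Assume D = 1.0 to 1.5 mm.
- Arm with f = 3%: 0.03 × 1.0 = 0.030 mm, to 0.03 × 1.5 = 0.045 mm.
- Arm with f = 2%: 0.02 × 1.0 = 0.020 mm, to 0.02 × 1.5 = 0.030 mm.
- Bias in the comparison: 0.030 − 0.020 = 0.010 mm, to 0.045 − 0.030 = 0.015 mm.

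Over a wider range (f from 1% to 5%, D from 0.5 to 2.0 mm), one arm's mean moves by 0.01 × 0.5 = 0.005 mm to 0.05 × 2.0 = 0.10 mm. With equal f and D in both arms, the bias in the comparison is zero.

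**4. Size for responders.** If r is the rate among evaluable subjects, counting the replaced as non-responders gives r × (1 − f): 0.98r at f = 2% and 0.97r at f = 3%.

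**5. What a count by arm can show.** Assume 250 per arm (1:1 split of 500, not stated in the documents). Replacement risks of 1%, 2%, 3% and 5% give 2.5, 5, 7.5 and 12.5 expected events per arm. Power to detect a doubling at two-sided 0.05 is 15%, 26%, 37% and 57%. Such a table would be descriptive.

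**The case against.** The strongest reply is that the plan already shows replacement, and much of it stands.
- Replacement has its own discontinuation reason, and SAP 8.1 tabulates discontinuations by treatment group.
- Elective knee surgery is prohibited (Protocol 7.6), so a replacement may also appear among the deviations. Procedures have their own eCRF and listing (Protocol 7.5, SAP 12.1).
- The AE carve-out depends on a judgement, does not name replacement, and is contradicted by neighbouring text. Unanticipated worsening can reach the target-knee AE table and the table of AEs leading to withdrawal.
- Worsening is partly visible: SAP 7.1 summarises change by group and visit with median, minimum and maximum, and mJSW change is itself a measure of progression.
- The waiver covers only subjects who leave after surgery. Those who leave before it owe a full Termination Visit, with a radiograph if none was taken in the preceding 12 weeks. A replacement after Visit 3E does not affect the FAS result at Visit 3E.
- Entrants completed the parent study, and planned knee surgery is an exclusion example, which may keep early replacements few.

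A reader might infer that knee worsening is taken out of safety counting altogether, that no table shows replacement, or that an imbalance could not be seen. The points above rule out all three.

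They do not settle the narrower matter. A disposition entry depends on which reason the site records, and replacement competes there with lack of efficacy and withdrawal by the subject. It does not govern the efficacy estimates, and none of the planned sensitivity analyses departs from MAR for these subjects.

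**Conclusion.** The point holds in limited form. Anticipated target-knee worsening, including worsening that leads to replacement, can be left out of AE and SAE counts, under text that conflicts with itself and with the knee-examination rule. Replacement should be visible by arm through disposition when it is recorded as the reason, and may appear elsewhere. No endpoint, estimand or efficacy analysis counts it, and the 6-month follow-up has no planned analysis. Subjects who leave after replacement before Visit 3E normally drop out of the main ANCOVA and the responder denominators, or are imputed as ordinary.

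The direction favours the arm with more replacements, provided that those subjects would have fared worse than the rest. The size is unknown. The 0.010 to 0.015 mm rests on an assumed 3% against 2% and an assumed 1.0 to 1.5 mm, and only the between-arm difference matters. The documents do not support calling this a large bias. It is a gap in a second-year safety and efficacy plan that is cheap to close.

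**What to change.** 1. **SAP 9.6.3:** count a subject with target-knee replacement before the visit as a non-responder in the improvement, strict-responder and PASS analyses.
2. **SAP Appendix 2:** name target-knee replacement as an intercurrent event, with a composite strategy for the responder endpoints and a non-MAR sensitivity analysis, for example worst-rank, for mJSW at Visit 3E.
3. **SAP section 10:** add a descriptive table of target-knee replacements by treatment group and period, whatever their AE classification, from the disposition and procedure eCRFs, with the 6-month follow-up where it was obtained.
4. **Protocol 8.1.1, 8.1.2 and 7.1.1:** reconcile the sentences on anticipated deterioration, clinically significant worsening, knee-examination findings and admissions. Which AE rule should apply is for the sponsor to decide.

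The cost is slightly lower responder rates, one extra table and one sensitivity analysis. Items 1 to 3 need only SAP wording and mostly data already collected; the 6-month follow-up may be incomplete, since the protocol asks only for an attempt. SAP 4.4 says the sponsor was unblinded once the parent-study database was locked, so if results by arm have been seen, the additions should be labelled post hoc.
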